8.1.4.1 Guidelines for management of elevated liver enzymes

Participants with signs or symptoms consistent with liver injury (eg, nausea, vomiting, anorexia, fatigue, or right upper abdominal pain or discomfort) should undergo immediate testing of ALT, AST, gamma-glutamyl transferase, bilirubin, alkaline phosphatase, prothrombin time, and international normalized ratio.

In the absence of clinical symptoms, participants with ALT or AST $>3 \times ULN$ (if normal at baseline) or >2-fold change (if abnormal at baseline) should be retested within 48 to 72 hours for the usual serum measurements (ALT, AST, alkaline phosphatase, and bilirubin) to confirm the abnormalities and to determine if the associated values are increasing or decreasing. There should also be an inquiry about symptoms at the time of follow-up.

If the above abnormalities are confirmed:

- Repeat liver enzyme and serum bilirubin tests 2 or 3 times weekly. The frequency of retesting can decrease to once a week or less if abnormalities stabilize or the study drug has been discontinued and the participant is asymptomatic;
- Obtain a more detailed history of symptoms and prior or concurrent diseases;
- Obtain a history of concomitant drug use (including nonprescription medications and herbal and dietary supplement preparations), alcohol use, recreational drug use, and special diet;
- Rule out acute viral hepatitis types A, B, C, D, and E; autoimmune or alcoholic hepatitis; nonalcoholic steatohepatitis; hypoxic/ischemic hepatopathy; and biliary tract disease;
- Obtain a history of exposure to environmental chemical agents;
- Obtain additional tests to evaluate liver function, as appropriate (eg, international normalized ratio, direct bilirubin); and
- Consider gastroenterology or hepatology consultations.

Study drug discontinuation should occur if:

- ALT or AST $> 8 \times ULN$;
- ALT or AST >5 × ULN for more than 2 weeks;
- ALT or AST >3 × ULN and total bilirubin >2 × ULN or international normalized ratio >1.5; or
- ALT or AST $>3 \times$ ULN with the appearance of fatigue, nausea, vomiting, right upper quadrant pain or tenderness, fever, rash, and/or eosinophilia (>5%).

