4.2 Exclusion Criteria

Participants who meet any of the following criteria will be excluded from participation in the study:

- 1. Have current or any previous history of New York Heart Association class III or IV heart failure or left ventricular ejection fraction <30%;
- 2. Have been hospitalized for heart failure within 5 years prior to Screening (Visit 1);
- 3. Have had any of the following clinical events within 3 months prior to Screening (Visit 1):
 - o Non-fatal MI;
 - Non-fatal stroke;
 - Non-elective coronary revascularization; and/or
 - Hospitalization for unstable angina and/or chest pain.
- 4. Have uncontrolled severe hypertension, defined as either systolic blood pressure ≥160 mmHg or diastolic blood pressure ≥100 mmHg at both Screening (Visit 1) and Randomization (Visit 2 [Day 1]) taken as the average of triplicate measurements. One triplicate retest will be allowed during the same visit, at which point if the retest result is no longer exclusionary, the participant may be randomized;
- 5. Have a formal diagnosis of homozygous FH;
- 6. Have active liver disease, defined as any known current infectious, neoplastic, or metabolic pathology of the liver; Child-Pugh score of 7 to 9 (Class B) or 10 to 15 (Class C); unexplained elevations in alanine aminotransferase (ALT) or aspartate aminotransferase (AST) > 3 × upper limit of normal (ULN); or total bilirubin > 2 × ULN at Screening (Visit 1);
 - Note: An abnormal ALT, AST, or total bilirubin must be confirmed by a repeat abnormal measurement at least 1 week apart.
- 7. Have a glycosylated hemoglobin (HbA1c) ≥10.0% (≥0.100 hemoglobin fraction) or a fasting glucose ≥270 mg/dL (≥15.0 mmol/L) at Screening (Visit 1);
- 8. Have thyroid-stimulating hormone $\geq 1.5 \times ULN$ at Screening (Visit 1);
- 9. Have creatine kinase (CK) $>3 \times$ ULN at Screening (Visit 1);
- 10. Have a history of a malignancy that required surgery (excluding local and wide local excision), radiation therapy, and/or systemic therapy during the 3 years prior to Randomization (Visit 2 [Day 1]);
- 11. Have a known history of alcohol and/or drug abuse within 5 years prior to Randomization (Visit 2 [Day 1]);
- 12. Have received treatment with other investigational products or devices within 30 days of Screening (Visit 1) or 5 half-lives of the previous investigational product, whichever is longer;

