 - Note: Participants who have received treatment for COVID-19 with standard of care and/or emergency use authorization medications, including vaccinations and boosters, within 30 days of Screening (Visit 1) or 5 half-lives of the previous investigational product **will** be permitted.
- 13. Are taking gemfibrozil or have taken gemfibrozil within 30 days of Screening (Visit 1);

- 14. Are taking ezetimibe or have taken ezetimibe within 14 days of Screening (Visit 1);
- 15. Have planned use of other investigational products or devices during the course of the study;
- 16. Have participated in any clinical study evaluating obicetrapib;
- 17. Have a known allergy or hypersensitivity to the study drugs, placebo, or any of the excipients in the study drugs or placebo; or
- 18. Have any participant condition that, according to the Investigator, could interfere with the conduct of the study, such as, but not limited to, the following:
 - o Are unable to communicate or to cooperate with the Investigator;
 - Are unable to understand the protocol requirements, instructions and study-related restrictions, and the nature, scope, and possible consequences of the study (including participants whose cooperation is doubtful due to drug abuse or alcohol dependency);
 - Are unlikely to comply with the protocol requirements, instructions, and study-related restrictions (eg, uncooperative attitude, inability to return for follow-up visits, and improbability of completing the study);
 - o Have any medical or surgical condition which, in the opinion of the Investigator, would put the participant at increased risk from participating in the study; or
 - o Are directly involved in the conduct of the study.

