Clinically significant abnormal laboratory or other examination findings (eg, ECG) that are detected during the study or are present at the date of the first dose of study treatment and significantly worsen during the study should be reported as AEs, as described below. The Investigator will exercise his or her medical and scientific judgment in deciding whether an abnormal laboratory finding or other abnormal assessment is clinically significant. Clinically significant abnormal laboratory values occurring during the study will be followed until repeat tests return to normal, stabilize, or are no longer clinically significant. Abnormal test results that are determined to be an error should not be reported as an AE. Laboratory abnormalities or other abnormal clinical findings (eg, ECG abnormalities) should be reported as an AE if any of the following are applicable:

- If an intervention is required as a result of the abnormality;
- If action taken with a study drug is required as a result of the abnormality; or

• Based on the clinical judgment of the Investigator.

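### Protocol 8.1.4.1: with a baseline ALT or AST above 2.5 × ULN, an asymptomatic value at the level of the 2-week stopping rule can fall short of the timed retest trigger

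*Protocol*

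**What the plan says.** Protocol 8.1.4.1 is guidance, worded mostly with should. Participants with symptoms of liver injury are tested at once. Without symptoms, the retest trigger depends on baseline: ALT or AST above 3 × ULN ("if normal at baseline) or >2-fold change (if abnormal at baseline) should be retested within 48 to 72 hours". If the retest confirms the abnormality, the instruction is "Repeat liver enzyme and serum bilirubin tests 2 or 3 times weekly", with the relaxation that "The frequency of retesting can decrease to once a week or less if abnormalities stabilize" or once study drug has stopped and the participant has no symptoms.

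The stopping criteria in the same section are all absolute. One has a duration: "ALT or AST >5 × ULN for more than 2 weeks". The others are above 8 × ULN, above 3 × ULN with raised bilirubin or INR, and above 3 × ULN with listed symptoms or eosinophilia.

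On entry, exclusion criterion 6 (Protocol 4.2) removes "unexplained elevations in alanine aminotransferase (ALT) or aspartate aminotransferase (AST) > 3 × upper limit of normal (ULN") at Screening, subject to a confirming repeat. It also removes "any known current infectious, neoplastic, or metabolic pathology of the liver; Child-Pugh score of 7 to 9 (Class B") or Class C. Criterion 18 excludes those who "Have any medical or surgical condition which, in the opinion of the Investigator, would put the participant at increased risk" from taking part.

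Three other provisions bear on follow-up. Protocol 8.1 states: "Clinically significant abnormal laboratory values occurring during the study will be followed until repeat tests return to normal, stabilize", or lose clinical significance. Protocol 6 permits unscheduled visits at the Investigator's judgment. Protocol 4.5 allows permanent discontinuation for a severe laboratory abnormality when the Investigator considers continued treatment not in the participant's interest.

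**The concern.** A rule that depends on persistence beyond 2 weeks needs at least two measurements. The retest trigger is what supplies the second one on a timetable. In participants with a raised baseline the trigger moves up with the baseline while the stopping level stays fixed, so above some baseline the trigger lies higher than the level it should help to assess.

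The ordering is also odd. A participant with a normal baseline is retested from just above 3 × ULN. One who starts at 3.0 × ULN and reaches 5.9 × ULN is not, although the second value is higher and is already at a level that the protocol names as a reason to stop if it lasts.

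What is at stake is individual safety monitoring: whether the 2-week rule can be assessed in time in this range would depend on the Investigator choosing to repeat the test.

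**Working it through.** The plan gives no figure to reproduce here. The check is of threshold logic in multiples of ULN.

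**Inputs**
- Abnormal-baseline trigger: more than 2-fold change (Protocol 8.1.4.1).
- Level of the persistence rule: above 5 × ULN (Protocol 8.1.4.1).
- Highest baseline counted: 3 × ULN, from exclusion criterion 6 (Protocol 4.2).
- Scheduled chemistry: Screening, Day 1, Day 28 (±7), Day 84 (±7), Day 112 (±7) and EOT (Protocol Appendix A).

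**Step 1: where the two rules separate.** Let b be baseline and x the on-study value of the same enzyme, both divided by ULN. Take the 2-fold change to mean x > 2b. A value at the stopping level that does not trigger the retest satisfies 5 < x ≤ 2b. Such values exist only if 2b > 5, that is b > 2.5.

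**Step 2: width of the range.** As a fold change from baseline, the range runs from 5/b to 2.

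| Baseline b (× ULN) | Trigger 2b | Stopping-level values not triggering | As fold change | Lower of 2b and 5 |
|---|---|---|---|---|
| 1.5 | 3.0 | none | – | 3.0 |
| 2.0 | 4.0 | none | – | 4.0 |
| 2.5 | 5.0 | none | – | 5.0 |
| 2.6 | 5.2 | 5.0 to 5.2 | 1.92 to 2.0 | 5.0 |
| 2.8 | 5.6 | 5.0 to 5.6 | 1.79 to 2.0 | 5.0 |
| 3.0 | 6.0 | 5.0 to 6.0 | 1.67 to 2.0 | 5.0 |

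Example: baseline 2.8 and a Day 28 value of 5.5 × ULN, against a trigger of above 5.6.

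**Step 3: can such baselines enter?** Yes, within limits. The enzyme limit in criterion 6 removes only values above 3 × ULN, so 2.5 to 3 × ULN passes unless known liver pathology, Child-Pugh class or the Investigator's view under criterion 18 excludes the participant. Baseline is the last pre-dose value (Protocol 9.2), so an explained elevation or a rise between Screening and Day 1 could exceed 3 × ULN. Those cases are not counted here.

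**Step 4: time to the next scheduled test.** From Day 28 to Day 84 is 84 − 28 = 56 days. With windows it is 77 − 35 = 42 to 91 − 21 = 70 days. Beyond the 14-day point of the rule, that is 56 − 14 = 42 days (42 − 14 = 28 to 70 − 14 = 56). Day 28 is the only scheduled chemistry during dosing before Day 84, when dosing ends.

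**Step 5: sensitivity to the reading.** If a 2-fold change meant an increase of more than 2 × baseline, the trigger would be x > 3b. The range would then open at b > 5/3 = 1.67, and at b = 3.0 it would run from 5 to 8 × ULN, where the immediate stop takes over. The reading used here is the narrower one.

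**Step 6: comparison within the protocol.** The CK guideline (8.1.4.2) requires a repeat above an absolute 5 × ULN whatever the baseline. The renal guideline (8.1.4.4) joins a relative fall in eGFR with an absolute floor of 15 mL/min/1.73 m². The abnormal-baseline liver limb has no absolute part.

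**The case against.** The strongest reply is that the protocol does not leave such a value unattended. Protocol 8.1 is directive: once a laboratory value is judged clinically significant, it will be followed with repeat tests. A value of 5 to 6 × ULN is already an event of special interest under 8.1.4 (above 3 × ULN at any baseline), so few Investigators would call it insignificant. Protocol 4.5 offers a route to discontinuation with no 2-week condition. The other enzyme can trigger the full retest on its own. The stopping rule applies whatever prompted the test. Finally, a trigger for change and a limit for stopping serve different purposes, and the section is guidance.

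Most of this stands, and it rules out a stronger reading. A reader might infer that nothing in the protocol directs a repeat test in this range, or that such a participant would simply stay on drug until Day 84. The documents do not support that: 8.1 directs follow-up once significance is judged, 6 permits an extra visit, and 4.5 permits stopping.

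What remains is narrower. Each of those routes starts with an Investigator's decision, and none sets a time. The special-interest review in 8.1.4 works through the databases and directs no retest. In this range no provision gives an automatic or timed repeat.

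**Conclusion.** The point holds in a narrow form. It needs all of the following: no symptoms; a baseline above 2.5 × ULN; a value of that enzyme above 5 × ULN but not above 2 × baseline; the other enzyme not triggering; and no other stopping criterion met. For baselines up to 3 × ULN the values concerned lie between 5 and 6 × ULN at most, which are rises of at least 1.67-fold and no more than 2-fold. The 2.5 × ULN cut-off rests on reading the 2-fold change as a value above 2 × baseline.

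A single value above 5 × ULN does not itself meet the stopping rule, so this is a gap in timed monitoring and not a breach of that rule. The documents do not say how many participants would have such baselines; the number is probably very small. No efficacy analysis is touched. It is a minor safety point, worth making because the remedy is cheap.

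**What to change.** In Protocol 8.1.4.1, define the abnormal-baseline trigger as a value above 2 × baseline or above 5 × ULN, whichever is lower. Every value above 5 × ULN in an asymptomatic participant then enters the 48 to 72 hour retest and, if confirmed, the repeat testing that follows. On the reading used here, the trigger is unchanged for baselines up to 2.5 × ULN and fixed at 5 × ULN above that. Naming a multiple of baseline also removes the ambiguity in the fold-change wording. If the authors meant an increase of more than 2 × baseline, they should know that this wording lowers the trigger for all abnormal baselines.

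The cost is one line of protocol text and a few extra retests in participants with baselines above 2.5 × ULN; for baselines up to 3 × ULN these would be for rises of 1.67- to 2-fold.

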8.1.4.2 Guidelines for monitoring and management of creatine kinase

If at any time after Randomization (Visit 2 [Day 1]) a participant experiences a CK elevation >5 × ULN, the participant will undergo a repeat confirmatory assessment as soon as is reasonably possible, preferably within 3 to 7 days of the laboratory result becoming available.

A repeat CK assessment will include query for related symptoms.

If the repeat CK assessment confirms an unexplained (ie, not associated with recent trauma or physically strenuous activity) CK abnormality >5 × ULN and the participant is asymptomatic, he/she should receive further assessment and investigation into the cause, assessment of whether there is renal injury, and measurement of CK approximately weekly, or more frequently if clinically indicated, until resolution. If CK levels continue to rise, the study drug should be discontinued.

If the participant experiences a CK elevation $>5 \times \text{ULN}$ and is symptomatic, the following should be completed:

- Interruption of study drug;
- Clarification of the nature, duration, and intensity of muscle symptoms;
- Review of possible predisposing factors, such as unaccustomed exercise, heavy alcohol intake, and viral illness (consider performing serology);
- Evaluation for additional diagnoses or other conditions which can cause myopathy, including muscle tenderness (by physical examination), weakness, rash, measurement of serum creatinine, and/or urine dipstick analysis with microscopy if indicated;
- Measurement of clinical chemistries to assess the possibility of lactic acidosis; and
- Follow-up of symptoms and CK until the abnormality has resolved.

If, based on the above evaluation, an alternative explanation is suspected, consideration can be given to resuming study drug once CK returns to baseline levels.

If no alternative explanation exists, consideration should be given to discontinuing study drug treatment.

If the repeat CK assessment confirms an unexplained (ie, not associated with recent trauma or physically strenuous activity) $CK > 10 \times ULN$, the participant should be discontinued from study drug, even in the absence of symptoms. The signs and symptoms and laboratory assessments as outlined above should also be evaluated. The participant should continue being followed in the study for safety.

Any event of rhabdomyolysis, regardless of CK level, should lead to study drug interruption or discontinuation until the contribution of obicetrapib has been excluded.

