3.1.2 Treatment Period

Up to 2 weeks after Screening (Visit 1), participants will return to the site on Visit 2 (Day 1) and confirm study eligibility before being randomized and beginning treatment. Approximately 400 eligible participants (100 participants per treatment group) will be randomized in a 1:1:1:1 ratio to 1 of the following treatment groups:

- FDC therapy: Obicetrapib 10 mg + ezetimibe 10 mg;
- Obicetrapib monotherapy: Obicetrapib 10 mg;
- Ezetimibe monotherapy: Ezetimibe 10 mg; or
- Placebo.

Approximately 70% of the participants enrolled into this study should be taking HIS. No more than approximately 10% of participants in this study will be completely statin intolerant.

Participants without underlying HeFH or a history of ASCVD but with multiple ASCVD risk factors will comprise a maximum of 30% of the total participants enrolled into the study. Participants with only HeFH will comprise a maximum of 20% of the total participants enrolled into the study.

During the 12-week Treatment Period, the assigned study drugs will be administered by the participants orally with water, with or without food, once daily on Day 1 to Day 84 at approximately the same time each morning. Participants will return to the site on Visit 3 (Day 28) (±7 days) and Visit 4 (Day 84) (±7 days) for efficacy and safety assessments. Participants, Investigators, the Clinical Research Organization, and the Sponsor will be blinded to all lipid results from Day 1 (Visit 2) for the first participant until the database is locked in order to protect blinding to treatment assignment.

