4.5 Withdrawal Criteria

A participant may prematurely discontinue study drug and/or withdraw from the study at any time. However, a distinction must be made between premature discontinuation of study drug and withdrawal from the study. All efforts should be made to ensure the participant continues in the study per protocol. If a participant discontinues study drug prior to completion of the study, all efforts will be made to continue to follow the participant and collect data for all visits.

Only participants that request discontinuation from the study and withdraw consent will be considered withdrawn from the study. For safety reasons, it will be recommended that all participants who withdraw from the study complete an End of Treatment (EOT) Visit. Withdrawn participants will not be replaced.

Participants may need to discontinue study drug during the course of the study. All efforts will be made to restart the study drug; however, in the event of the following, participants may be permanently discontinued from study drug:

- Occurrence of any medical condition or circumstance that exposes the participant to substantial risk and/or does not allow the participant to adhere to the protocol-specified study drug treatment regimen;
- Any SAE, clinically significant AE, severe laboratory abnormality, intercurrent illness, or other medical condition, which indicates to the Investigator that continued treatment with study drug is not in the best interest of the participant;
- Pregnancy; or
- Requirement of prohibited concomitant medication.

If a participant permanently discontinues study drug, he/she will continue to participate in study visits as described below:

- If a participant discontinues study drug between Visit 2 (Day 1) and Visit 3 (Day 28) or at Visit 3 (Day 28), he/she should complete an EOT Visit at Day 28, return to complete Visit 4 (Day 84), and return to complete the Safety Follow-up Visit (Day 112); or
- If a participant discontinues study drug between Visit 3 (Day 28) and Visit 4 (Day 84), he/she should return for Visit 4 (Day 84) and the Safety Follow-up Visit (Day 112) as scheduled.

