5 STUDY TREATMENTS

5.1 Treatment Groups

Participants will be randomized in a 1:1:1:1 ratio to 1 of the following treatment groups:

- FDC therapy: Obicetrapib 10 mg + ezetimibe 10 mg (administered as 1 obicetrapib 10 mg + ezetimibe 10 mg FDC tablet, 1 obicetrapib-matched placebo tablet, and 1 ezetimibe-matched placebo capsule);
- Obicetrapib monotherapy: Obicetrapib 10 mg (administered as 1 FDC-matched placebo tablet, 1 obicetrapib 10 mg tablet, and 1 ezetimibe-matched placebo capsule);
- Ezetimibe monotherapy: Ezetimibe 10 mg (administered as 1 FDC-matched placebo tablet, 1 obicetrapib-matched placebo tablet, and 1 ezetimibe 10 mg capsule [over-encapsulated 10 mg tablet]); or
- Placebo (administered as 1 FDC-matched placebo tablet, 1 obicetrapib-matched placebo tablet, and 1 ezetimibe-matched placebo capsule).

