5.4 Breaking the Blind

Study drugs will be managed using the IRT system. Each user will have a unique username and passcode to access the system. Investigators shall not break the study blind during the study, and Investigators should treat all participants as if they had received obicetrapib or ezetimibe. However, in situations in which knowledge of the participant's study drugs is necessary for clinical management, the Investigator should proceed with unblinding.

Once a participant's treatment assignment has been unblinded, the Medical Monitor or designee should be notified within 24 hours of unblinding of the treatment. Information relating to unblinding (eg, date and time of the call to the Medical Monitor by the Investigator, reason for unblinding, and date and time of unblinding) shall be clearly recorded in the participant's study file and in the electronic data capture (EDC) system, as part of relevant standard operating procedures. In addition, the Investigator should consider whether the clinical event prompting unblinding should be considered an AE or SAE, according to the regulatory definitions or criteria for AEs or SAEs, and if so, submit an AE/SAE report to the Sponsor or designee (see Section 8.3). The Sponsor or designee will also unblind any SAE reports that are unexpected and considered to be related to the study drugs, in accordance with safety reporting guidance and regulations.

Each study site will be provided with a sealed envelope containing a 6-digit code that can be entered into the IRT system to unblind a participant's treatment assignment.

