5.5.2 Study Drug Preparation and Dispensing

At Visit 2 (Day 1), participants will receive 1 kit (containing 36 FDC tablets or matching placebo tablets, 36 obicetrapib tablets or matching placebo tablets, and 36 ezetimibe capsules or matching placebo capsules totaling 108 tablets/capsules per kit) with the study drugs appropriate for the participant's treatment group. At Visit 3 (Day 28), participants will receive 2 kits as described above. The 2 kits provide sufficient supplies for 56 days of dosing, with enough for an extra 16 days of dosing in case the participant needs to postpone Visit 4 (Day 84). Each individual kit will provide a sufficient supply for 28 days of dosing, with enough for an extra 8 days of dosing. Participants will be instructed to take 3 units from the kit each day. The kit will be clearly labelled to indicate which tablets and capsule to use on each day. Participants will be instructed to bring all unused study drugs to the site at the next visit.

This study protocol includes contingency measures to manage disruptions due to COVID-19 control measures, including modifications to dispensation of the study drugs specific to situations where COVID-19 is impacting study conduct. See Section 3.1.4 for details of COVID-19 contingency measures. In the absence of a COVID-19 impact, it is expected that Investigators and participants follow the protocol requirements as set forth.

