8.1.2 Unexpected Adverse Drug Reaction

An Unexpected Adverse Drug Reaction is defined as an adverse reaction, the nature or severity of which is not consistent with the applicable product information.

For the obicetrapib 10 mg + ezetimibe 10 mg FDC, the reference safety information is included in Section 6 of the Investigator's Brochure currently in force. The reference safety information will be reviewed annually by the Sponsor and the periodicity of the review will be harmonized with the reporting period of the Development Safety Update Report, where possible.

For ezetimibe, the reference safety information is included in the Summary of Product Characteristics.

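### After rhabdomyolysis, Protocol 8.1.4.2 requires only obicetrapib to be excluded before the study drug hold ends, although 2 of the 4 blinded arms take ezetimibe

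*Protocol*

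**What the plan says.** The last sentence of Protocol 8.1.4.2 sets a rule for rhabdomyolysis that applies at any CK value: "Any event of rhabdomyolysis, regardless of CK level, should lead to study drug interruption or discontinuation until the contribution of obicetrapib has been excluded". The hold covers study drug as a whole, but its end is tied to one product.

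Other parts of the protocol bear on this:

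- **Arms (5.1).** Ezetimibe is in the fixed dose combination (FDC) arm and in the ezetimibe monotherapy arm. The latter is given as "1 FDC-matched placebo tablet, 1 obicetrapib-matched placebo tablet, and 1 ezetimibe 10 mg capsule", so it contains no obicetrapib.
- **Allocation (3.1.2).** "Approximately 400 eligible participants (100 participants per treatment group) will be randomized in a 1:1:1:1 ratio".
- **Management under the blind (5.4).** "Investigators should treat all participants as if they had received obicetrapib or ezetimibe". Where knowledge of the allocation "is necessary for clinical management, the Investigator should proceed with unblinding".
- **Dosing (5.5.2).** "Participants will be instructed to take 3 units from the kit each day". Resuming study drug therefore resumes whatever active drug the kit holds.
- **Reference safety information (8.1.2).** "For ezetimibe, the reference safety information is included in the Summary of Product Characteristics". The protocol thus treats ezetimibe as a product with its own safety profile.

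**The concern.** The rule protects a participant who has had a serious muscle event from re-exposure before the possible cause has been examined. In a trial of two active drugs it should cover both. As worded, a site can satisfy it while leaving ezetimibe out of account and then hand back a kit that contains ezetimibe.

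The wording also stands apart from its neighbours. The liver, CK and renal stopping rules in 8.1.4.1, 8.1.4.2 and 8.1.4.4 speak of study drug without singling out a product. Only the rhabdomyolysis sentence names one. What is at stake is participant safety and consistent handling across approximately 60 sites. Efficacy inference is not at stake.

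**Working it through.** The plan gives no figure on this point to reproduce. The check is a count of arms, followed by a reading of the release condition arm by arm.

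**Count.** Inputs: 400 planned participants, four arms, equal allocation (3.1.2); contents of each arm (5.1).

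- Per arm: 400 / 4 = 100.
- Arms with ezetimibe: FDC and ezetimibe monotherapy = 2 of 4; 2 × 100 = 200; 200 / 400 = 50%.
- Arms with ezetimibe and no obicetrapib: 1 of 4; 100 / 400 = 25%.
- On any active study drug: 3 × 100 = 300. Share for whom ezetimibe is the only one: 100 / 300 = 33%.

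These are shares of allocation, not risks. If one event occurred and the arms did not differ (an assumption), the chance that the participant was on ezetimibe would be 0.50, and on ezetimibe alone 0.25. The argument does not depend on those chances.

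**Release condition by arm, if the participant is unblinded.**

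| Arm | Obicetrapib excluded by allocation? | Active study drug the rule leaves unaddressed |
|---|---|---|
| FDC | No | Ezetimibe |
| Obicetrapib monotherapy | No | None |
| Ezetimibe monotherapy | Yes | Ezetimibe, the only active study drug |
| Placebo | Yes | None |

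In the ezetimibe monotherapy arm the condition is met as soon as the allocation is known. In the FDC arm obicetrapib must still be cleared on clinical grounds, but ezetimibe need not be.

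**If the participant stays blinded.** Should a clear unrelated cause be found, both drugs are in effect cleared and the wording does no harm. Should the Investigator instead reason only that obicetrapib is not implicated, the condition is met with ezetimibe unaddressed. That is at odds with the instruction in 5.4.

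**Does another rule in 8.1.4.2 close the gap?** For symptomatic CK above 5 × ULN, resumption is considered when an alternative explanation is suspected and CK is back to baseline. An unexplained, confirmed CK above 10 × ULN requires discontinuation. Neither rule is limited to obicetrapib, so above those triggers they give partial cover. The rhabdomyolysis sentence, however, also reaches events below them, where the CK resumption test does not apply.

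**The case against.** The strongest reply is that ezetimibe will be considered anyway.

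- Section 8.1.3 has the Investigator judge each adverse event against the study drugs, and 5.5.1 counts ezetimibe capsules and FDC tablets among these.
- The CK rules already restrict resumption.
- The rhabdomyolysis sentence sets a minimum hold on all study drug and does not order a restart.
- Section 4.5 lets the Investigator stop permanently after a serious or clinically significant event.
- The clearest failure needs a chain of steps: rhabdomyolysis, unblinding, allocation to ezetimibe monotherapy, and an Investigator who then restarts without thinking about ezetimibe. Unblinding must also be notified to the Medical Monitor within 24 hours.

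All of this stands as a limit on the practical risk. None of it changes the release condition, which remains incomplete for half the planned participants.

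Three stronger readings are tempting, and the documents do not support them:

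- **That ezetimibe is a known cause of rhabdomyolysis here.** The documents give no evidence on this. Section 1.5.1 describes ezetimibe's safety favourably, and the product information cited in 8.1.2 is not reproduced. The point rests on the protocol's internal consistency alone.
- **That 4.5 pushes sites to restart after the combined liver stop (ALT or AST with bilirubin or INR).** Section 4.5 does say "All efforts will be made to restart the study drug; however, in the event of the following, participants may be permanently discontinued from study drug". But the list that follows includes severe laboratory abnormalities and substantial risk to the participant, and 8.1.4.1 itself calls for discontinuation. Permanence is left to the Investigator, which is a defensible choice. Making it mandatory for one of the four liver limits, with no allowance for another cause, would be a trade-off and not a correction.
- **That the permissive wording for pregnancy in 4.5 leaves a gap.** Section 8.4 already orders dosing to stop at once.

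**Conclusion.** The concern holds for the rhabdomyolysis rule only. Its release condition names one of the two active drugs, contrary to the management principle in 5.4. The omission bears on 2 of 4 arms (about 200 of 400 planned participants). It is sharpest in the ezetimibe monotherapy arm (about 100), where unblinding alone meets the condition.

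The counts rest on planned enrolment and equal allocation. The documents give no rate for rhabdomyolysis, so the number of participants affected is not estimated, and it may well be none. Existing safeguards make the practical risk small. This is a wording defect worth correcting because it concerns safety and the remedy is cheap. It has no bearing on the estimand, the imputation, the type I error rate or the power.

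**What to change.** In the last sentence of Protocol 8.1.4.2, change the closing condition so that the hold lasts *until the contributions of both obicetrapib and ezetimibe have been excluded*. No new visits or tests are needed. No change to the liver or pregnancy wording is proposed.

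**Cost.** A short protocol amendment with IRB approval (12.1), circulated to approximately 60 sites; it could be bundled with another amendment. Some participants may be held off drug longer when ezetimibe cannot be excluded. Day 84 data need not be lost, because 4.5 keeps participants who stop study drug in the visit schedule and the treatment policy estimand in 9.2.1.1 uses measurements taken after treatment stops.
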